The primary analysis will be performed on the Intention-to-Treat (ITT) Population, analyzing participants according to their randomization assignment regardless of potential exposure to the opposite assignment. The primary analysis will use multiple imputation to account for missingness of the primary outcome variable. See Section 14.10, Missing Data, for further details. A secondary analysis will be performed on the Per Protocol (PP) population. This population will exclude participants who had appointments with PCPs in the opposite treatment arm. A secondary analysis will adjust for individual-level covariates which may be associated with the response, such as demographic variables, baseline measures of risk behaviors, substance use, presence of alcohol or drug use disorder, pain ratings, mental health symptoms or conditions, and health-related quality of life. Details regarding selection of covariates for inclusion and potential transformations will be specified in the Statistical Analysis Plan (SAP).

A secondary analysis will fit the same model to the 180-day outcome measured at the 12-month timepoint in order to assess durability. Further secondary analyses will explore temporal patterns of number of days of risky opioid use. The 3-month (days of use in the first 90 days post-baseline) and 6-month (days of use in days 91-180 post-baseline) secondary outcome measures will

assess early intervention effects. The measures at 9 and 12 months will assess the durability of intervention effects (which may be maintained, increased, or decreased) over time.

Time trends of the mean number of days of use per 90 days will be visualized over the course of the year by treatment group with 95% confidence intervals. In addition, a mixed effects negative binomial model will be fit including treatment by time interactions for each timepoint. The model will include participant random intercepts to account for correlation in responses arising from multiple observations for each participant. Further details, including specification of the distributions of the random terms and possible inclusion of participant random slopes, will be specified in the SAP.

As month-to-month variability and temporal trends in the response are not known, this time trend analysis will be repeated for monthly observations of the 30-day sum of unhealthy days in order to further understand and describe temporal patterns.

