Fixed effects include treatment, piecewise linear function of time, interaction of treatment \times piecewise linear function of time, baseline risky opioid use and site. A random effect term for patient participants will be included to account for the correlation of repeated measures within the same patient participant and within-PCP correlation of participant responses. The autoregressive covariance structure will be used to take into account the correlation of the repeated measures of monthly risky opioid use. This structure specifies that observations that are more proximate to one another are more correlated than those that are more distant.

The following is an example of a model with piecewise linear functions at the breaking point of month 6 to allow the slopes that represent the change in the outcome over time to vary between Months 1-6 and Months 7-12.

The SAS code to create a linear spline variable to specify time spline “timespl” equal to “0” when time is from Months 1 to Month 6, or equal to “time – 6” when the time is greater than Month 6 is as follows.

```
DATA datmonthly;
  SET datmonthly;
  Chgpoint=6;
  If time <= Chgpoint then timespl=0;
  else if time >Chgpoint then timespl = time - 6;
RUN;
```

The model investigates whether there is treatment effect on change of monthly risky opioid use over 12 months. The estimates of time and piecewise linear time spline will provide information on the change of risky opioid use before and after Month 6. The interaction terms of treatment with time and time spline assess the difference in change of opioid use associated with the treatment effect during the two time segments. The “Estimate” statement is used to derive the following estimates and corresponding p-values:

1. Difference of time slopes in change of risky opioid use during Months 1-6 between the two treatment groups
2. Difference of time slopes in change of risky opioid use during Months 7-12 between the two treatment groups.

```
PROC GLIMMIX DATA=datmonthly METHOD=quad;
  CLASS PATID PCP time treat site;
  MODEL daysmonthly = treat time timespl treat*time treat*timespl site baseline / solution
  DIST=negbin LINK=log ddfm=bw;
  RANDOM intercept / SUBJECT= PCP;
  REPEATED / SUBJECT=PATID TYPE=AR(1);
  Estimate "Difference of change Months 1-6"
  time 0 timespl 0 treat*time 1 -1 treat*timespl 0 0/ CL ilink;
  Estimate "Difference of change Months 7-12"
  time 0 timespl 0 treat*time 1 -1 treat*timespl 1 -1/ CL ilink;
```

RUN:

where

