“datmonthly” is the name of the dataset with one row for each month of risky opioid use for each patient participant in a long format,

“daysmonthly” is the name of the outcome, a continuous variable indicating monthly use of risky opioid use (days),

“treat” is a binary indicator variable coded as “1” for intervention arm STOP and “0” for control arm EUC,

“time” is a continuous variable indicating the number of the month when the opioid use is collected,

“timespl” is a continuous variable equal to 0 when time is in Months 1-6, or equal to time – 6 when the time is months 7-12;

“baseline” is a continuous variable indicating the number of days of risky opioid use during past 30 days prior to baseline assessment,

“site” is a categorical variable for the 5 participating sites,

“month” is a categorical variable for month during the study,

“PATID” is a character variable representing patient participant ID, and

“PCP” is a character variable representing PCP clusters.

Comparison of the time trend measured by time slopes in change of risky opioid use in treatment arm STOP compared to EUC during Months 1-6 and Months 7-12 separately will be reported as the estimated risk ratio along with a 95% confidence interval given the linear combination of estimated parameters shown in the Estimate statement.

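### The monthly trend template in SAP 7.6 lists time in CLASS, so its two slope differences are not estimable; it also lacks the promised patient random effect and its contrasts may run EUC minus STOP.

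*SAP*

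**What the plan says.** SAP 7.6 plans a mixed negative binomial model for the monthly counts, with a piecewise linear function of time interacting with treatment. The variable list after the code says that time "is a continuous variable indicating the number of the month when the opioid use is collected". The example places the knot at month 6: "If time <= Chgpoint then timespl=0", and time minus 6 afterwards.

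The template itself reads "CLASS PATID PCP time treat site", then "MODEL daysmonthly = treat time timespl treat*time treat*timespl site baseline / solution". Two ESTIMATE statements put `1 -1` on `treat*time`; the second adds `1 -1` on `treat*timespl`. The text says they yield the between-arm differences in slope for Months 1-6 and Months 7-12, reported as STOP compared with EUC, with STOP coded 1 and EUC coded 0.

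The variable list also defines a separate variable, month, which "is a categorical variable for month during the study". It appears nowhere in the code.

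On correlation, the SAP text says: "A random effect term for patient participants will be included to account for the correlation of repeated measures", together with an autoregressive structure. Protocol 14.6 says: "The model will include participant random intercepts to account for correlation in responses arising from multiple observations for each participant". The only RANDOM statement in the template is "RANDOM intercept / SUBJECT= PCP". A REPEATED statement with the patient as subject and an AR(1) type follows it.

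**The concern.** The same variable is continuous in the text and categorical in the code. With 12 months and a CLASS declaration, the month indicators and their interaction with arm already describe every arm-by-month mean, so no slope is left for the spline terms to estimate. The two rows that are meant to deliver the reported results then have nothing to act on.

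Table 42 depends on this template. Tables 47, 51, 55 and 59 repeat Table 42 for binge alcohol, benzodiazepines, stimulants and marijuana, so five results tables are affected. An analyst who finds that the template fails would have to rewrite a prespecified model with the data in hand. A partial repair that only takes time out of CLASS could leave every slope ratio inverted.

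**Working it through.** The documents give no figure for this analysis, so there is none to reproduce. The first three steps are algebra on the template; the fourth is a simulation with stated assumptions.

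**1. Size and rank of the fixed-effect design** (5 sites, 2 arms, 12 months, all from SAP 7.6).

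| | time in CLASS | time continuous |
|---|---|---|
| Intercept | 1 | 1 |
| treat | 2 | 2 |
| time | 12 | 1 |
| timespl | 1 | 1 |
| treat*time | 24 | 2 |
| treat*timespl | 2 | 2 |
| site | 5 | 5 |
| baseline | 1 | 1 |
| **Columns** | **48** | **15** |
| **Rank** | 24 cells + 4 sites + 1 baseline = **29** | 2 arms × 3 (level, slope, change of slope) + 4 + 1 = **11** |
| **Rank without spline terms** | **29** | 2 × 2 + 4 + 1 = **9** |

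With time in CLASS, dropping both spline terms does not change the rank: they are fully aliased. With time continuous they add 2. A numerical rank check gave the same values.

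**2. Estimability of the two ESTIMATE rows with time in CLASS.** A row is estimable only if it is a weighted sum of design rows. Let w(a,m) be the total weight on arm a, month m. The `treat*time` columns are indicators of the 24 cells, so w(a,m) must equal the `treat*time` coefficient of that cell. It follows that:
- the treat coefficient of arm a must be Σ over m of w(a,m);
- the time coefficient of month m must be Σ over a of w(a,m);
- the `treat*timespl` coefficient of arm a must be Σ over m of w(a,m) × max(0, m − 6).

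Months 1-6 row: the weights are +1 and −1 on the first two cells. If those are the two arms in month 1, the treat coefficients would have to be +1 and −1, but the row gives treat none. If they are months 1 and 2 of the first arm, the time coefficients would have to be +1 and −1, but the row sets time to 0. It fails in either column order.

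Months 7-12 row: it fails for the same reasons. In addition, months 1 and 2 have spline value 0, so the `treat*timespl` coefficients would have to be 0, but the row asks for +1 and −1. The `treat*timespl` difference taken alone is not estimable either.

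With time continuous, each arm has its own slope and change of slope, and both rows are estimable.

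**3. Direction of the contrast once time is continuous.** If level 0 (EUC) sorts first, `1 -1` is the EUC slope minus the STOP slope. With true STOP minus EUC slope differences of −0.04 and −0.01, the rows return +0.04 and +0.01. For the first, the reported ratio would be exp(0.04) = 1.041 instead of exp(−0.04) = 0.961.

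**4. Does omitting the patient term spoil the standard errors?** Monthly Binomial(30) counts were simulated with no arm difference. From SAP Section 10: mean 20/90 on the logit scale, PCP variance 0.15, patient variance 0.25, and 60 PCPs with 5 patients, taken as 4 analysed after 20% dropout. The fitted negative binomial models had continuous time with a knot at month 6, no site or baseline terms and no AR(1) term. The second row of the table adds an AR(1) process to the simulated data, with variance 0.25 and correlation 0.8; both are assumptions that the documents do not give. There were 100 runs per setting, so each ratio carries about 1/√(2 × 99) = 7% Monte Carlo error.

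Results with the PCP intercept only, as mean model SE / empirical SD:

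| Patient variation | Months 1-6 | Months 7-12 | Rejection at 5% |
|---|---|---|---|
| Pure random intercept | 0.0718/0.0492 = 1.46 | 0.0587/0.0411 = 1.43 | 1%, 0% |
| Plus assumed AR(1) | 0.0881/0.0825 = 1.07 | 0.0721/0.0661 = 1.09 | 5%, 5% |

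Replacing the PCP intercept with a patient intercept gave slope ratios of 1.22 and 1.19 (pure intercept) and 0.78 and 0.79 (assumed AR(1)). For the arm effect at month 6 the ratios were 0.73 and 0.70, with 17% and 16% rejection. A patient term therefore has to be added to the PCP term, not put in its place.

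**The case against.** The best defence is that this is example code for a supportive analysis and that the surrounding text is right: continuous time, piecewise slopes, a patient effect, autoregressive correlation. The Table 42 footnote leaves the final breakpoints to the data, so the code was not the last word. H1.2 is framed at 3, 9 and 12 months, and those comparisons come from the quarterly and 180-day models; the quarterly text declares time categorical, so CLASS time is right there. Non-estimable rows should also show up at the first run. All of this limits the consequence, and it stands. It does not remove the defect, because the CLASS line fails for any choice of breakpoint.

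A reader might go further and infer that the missing patient term makes the reported standard errors wrong. The documents do not support that. The template carries a patient-level AR(1) statement that matches the autoregressive structure in the text. Even with that statement ignored, keeping the PCP intercept gave slope standard errors from about right to too wide, so the simulation shows at worst lost precision for the slopes, not false positives.

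A reader might also expect a one-month contrast mislabelled as a slope. The rows are not estimable under either column order, so the template gives no valid estimate to mislabel. Whether REPEATED can be combined with quadrature estimation is a software question that was not tested and that the documents do not settle.

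**Conclusion.** Wrong as written. The non-estimability follows from the template alone and rests on no simulation: 48 columns, rank 29 with or without the spline terms, and neither stated slope difference obtainable; after the correction, 15 columns, rank 11, and both obtainable. The missing patient random effect is a plain mismatch between the code and both the SAP text and Protocol 14.6. The inverted contrast is conditional on EUC, coded 0, sorting first.

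No claim about the size of a standard-error fault should be attached. The range of about right to about 45% too wide depends on an assumed within-patient correlation and on ignoring the AR(1) statement.

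The reach is Table 42 and its four repeats for other substances. The primary analysis is unaffected.

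**What to change.** In the monthly template of SAP 7.6:
- Remove time from CLASS. If the AR(1) structure needs a class variable to order the months, use month, which is already defined.
- Keep the PCP intercept and add a patient-within-PCP random intercept, or state that the AR(1) structure replaces it and amend the text to match.
- Keep an autoregressive structure, since the text specifies one; simply deleting REPEATED would create a new conflict. Confirm the syntax and estimation method by running the template on dummy data.
- Set the contrasts to STOP minus EUC: `treat*time -1 1` for Months 1-6, and the same plus `treat*timespl -1 1` for Months 7-12, after checking the level order in the output.

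Align the random terms of the quarterly and 180-day models with the text in the same way. If categorical months are preferred, drop the spline terms and report month-specific ratios instead of slopes.

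The cost is SAP wording and one test run; no new data are needed.

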“daysin180” is the name of the primary outcome, a continuous variable indicating the number of days of risky opioid use within the first 180 days following the baseline assessment,

“treat” is a binary indicator variable coded as “1” for intervention arm STOP and “0” for control arm EUC,

“baseline” is a continuous variable indicating the number of days of risky opioid use during past 30 days prior to baseline assessment,

“site” is a categorical variable for 5 participating sites, and

“PCP” is a character variable representing PCP clusters.

The option method = quad indicates that the likelihood will be evaluated using the Gaussian quadrature method. Assessment of model fit will be reported based on standard goodness-of-fit metrics (e.g., deviance) and inspection of Pearson residuals.

The treatment effect of STOP from this model will be given as a rate ratio, the exponentiated estimate of the treatment effect, along with a 95% confidence interval. This can be interpreted as a ratio of the mean total number of days of risky opioid use for those enrolled to STOP versus EUC within the first 180 days post-randomization, when all other variables in the model are held constant. A risk ratio less than 1 would indicate fewer days of risky opioid use for those assigned to STOP compared to those assigned to EUC.

The primary outcome analysis will be performed on the Intent-to-Treat (ITT) Population, analyzing patient participants according to their PCP's randomization assignment regardless of potential exposure to the opposite assignment. The primary analysis will use multiple imputation to account for missingness of the primary outcome variable with details provided in Section 7.2.3.

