10.0 SAMPLE SIZE AND POWER

Power was based on simulations exploring four possible scenarios to consider different time trends of the intervention effect as well as possible assessment impact in the control group. Assessment impact means that the repeated monthly assessments alone could lead to a decrease in the control group in the response variable. The four scenarios are depicted in Figure 5. This figure shows the mean values of unhealthy days (within the past 90 days) assumed in each arm at 0, 3, and 6 months. The mean in the control arm is expected to be between 10 and 20, and 20 was selected for simulations because it is the most conservative (i.e., gives the lowest power), assuming that the additive effect size does not change as the control group mean changes. Scenario 1 has a 6-day constant difference between groups at both time points; in scenario 2 the intervention effect wanes to a 5-day difference during months 4-6. Scenarios 3 and 4 are the same as 1 and 2, but with assessment impact included, decreasing the mean by an additional 1 day per 90 days in each arm.

10.1 Figure 5: Mean Values in Treatment and Control Groups for Four Different Simulation Scenarios

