Quarterly Risky Opioid Use (Days)			
1-3 Months			
N	N		
Mean	X.X		
SD	X.XX		
Minimum	X		
Median	X.X		
Maximum	X		
4-6 Months			
...			
9-12 Months			
N	N		

Table 41: Summary Statistics of Risky Opioid Use by Treatment Arm

	Treatment Arm		Total (N=)
	EUC (N=)	STOP (N=)	
Mean	X.X		
SD	X.XX		
Minimum	X		
Median	X.X		
Maximum	X		
6-Months Risky Opioid Use (Days)			
1-6 Months			
N	N		
Mean	X.X		
SD	X.XX		
Minimum	X		
Median	X.X		
Maximum	X		
7-12 Months			
N	N		
Mean	X.X		
SD	X.XX		
Minimum	X		
Median	X.X		
Maximum	X		

Table 42: Summary of Risky Opioid Use in Past 30 Days by Treatment Arm

Treatment Arm	Number of Participants Enrolled	Number of Participants Contributing to Estimate for Monthly Use ¹		
EUC	N	N (X.x%)		
STOP				
Total				
Results²				
Time Duration	Rate Ratio	95% Lower Confidence Limit	95% Upper Confidence Limit	p-value
Months 1~6	X.xx	X.xx	X.xx	0.xxx
Months 7~12				

¹A participant contributes to the monthly use estimate if they have all fixed effect covariates and at least one monthly use outcome through 12 months post-baseline.

² Results are obtained from a longitudinal mixed effects model. Time trends of the treatment effect are modelled using a piecewise linear function for the time variable. The results are reported with the piecewise linear function at the breaking point of month 6 to allow for different slopes for the change in risky opioid use during months 1-6 and months 7-12. In final data analysis, the growth trajectory pattern of the change in opioid use during the 12-month study period will be used to determine the breaking points used in the final model.

Table 43: Summary of Risky Opioid Use in Past 90 Days by Treatment Arm

Treatment Arm	Number of Participants Enrolled	Number of Participants Contributing to Estimate during Months 1-3 ¹	Results ²						
			Rate Ratio	95% Lower Confidence Limit	95% Upper Confidence Limit	p-value			
EUC	N	N (X.x%)	X.xx	X.xx	X.xx	0.xxx			
STOP									
Total									
Months 4-6									
Treatment Arm	Number of Participants Enrolled	Number of Participants Contributing to Estimate during Months 4-6 ³	Results ⁴						
			Rate Ratio	95% Lower Confidence Limit	95% Upper Confidence Limit	p-value			
EUC	N	N (X.x%)	X.xx	X.xx	X.xx	0.xxx			
STOP									
Total									
Months 7-9									
Treatment Arm	Number of Participants Enrolled	Number of Participants Contributing to Estimate during Months 7-9 ⁵	Results ⁶						
			Rate Ratio	95% Lower Confidence Limit	95% Upper Confidence Limit	p-value			

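### The monthly 30-day model reports only a ratio of time slopes under the heading Rate Ratio, so its table cannot show whether STOP had fewer days of use

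*SAP*

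**What the plan says.** SAP 7.5 places days of risky opioid use in the past 30 days, measured monthly for 12 months, among the outcomes for H1.2, whose hypothesis is fewer days under STOP. SAP 7.7 lists the same monthly measure for H2.1-H2.4. SAP 7.6 says the monthly model will evaluate the treatment effect as well as variability and trends over time. Protocol 14.6 plans treatment-by-time interactions for each timepoint, with the time-trend analysis repeated on monthly data.

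The example model in SAP 7.6 has a knot at month 6: "MODEL daysmonthly = treat time timespl treat*time treat*timespl site baseline / solution". Two estimates are taken from it. The first is the "Difference of time slopes in change of risky opioid use during Months 1-6 between the two treatment groups"; the second is the same quantity for Months 7-12. Their coefficient rows are "time 0 timespl 0 treat*time 1 -1 treat*timespl 0 0/ CL ilink" and "time 0 timespl 0 treat*time 1 -1 treat*timespl 1 -1/ CL ilink". What is reported, as an estimated risk ratio with a 95% confidence interval, is the "Comparison of the time trend measured by time slopes in change of risky opioid use in treatment arm STOP compared to EUC".

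Table 42 in SAP 18.1 puts these two results in a column headed Rate Ratio, one row per segment. Its footnote says that the knot is there to "allow for different slopes for the change in risky opioid use during months 1-6 and months 7-12". Tables 47, 51, 55 and 59 repeat the shell for binge alcohol, benzodiazepines, stimulants and marijuana. Tables 43-45 use the same heading for ratios that combine the treatment main effect with its interaction with time.

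**The concern.** A hypothesis of fewer days is about the level of use in one arm relative to the other. A ratio of slopes is about whether that relative level is changing. If STOP lowers use by the first month and holds the gain, there is nothing for a slope contrast to detect.

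The heading adds to the difficulty. The Months 7-12 row of Table 42 and the result in Table 45 cover the same period under the same heading but are different quantities: one a per-month ratio of slopes, the other a ratio of total days. A reader who takes them for the same thing would see a value near or above 1 beside one well below 1 and could not tell why. Correcting the code alone would not remove the problem, because the text itself specifies slopes.

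**Working it through.** **1. The plan's own figure.** SAP 10.0: "Scenario 1 has a 6-day constant difference between groups at both time points". The 90-day means are 20, 20 (EUC) and 14, 14 (STOP). Over 180 days, 20 + 20 = 40 and 14 + 14 = 28, a difference of -12 days as the SAP states. The level ratio is 28/40 = 0.70.

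**2. What the two rows estimate.** Leave aside site, baseline and random terms, take time as continuous (as the text defines it), and let s = max(0, month - 6):

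log mean = b0 + b1·treat + b2·time + b3·s + b4·treat·time + b5·treat·s

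- STOP/EUC level ratio at month m: exp(b1 + b4·m + b5·s)
- Table 42, Months 1-6: exp(b4)
- Table 42, Months 7-12: exp(b4 + b5)

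The coefficient b1 appears in neither printed quantity. On this coding b1 is the log ratio extrapolated to month 0, so even the month 1 level needs b1 + b4.

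**3. Trajectories put through the model without noise.** The inputs are illustrative.

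| True STOP/EUC ratio of days | Printed, Months 1-6 | Printed, Months 7-12 |
|---|---|---|
| 0.70 throughout | 1.000 | 1.000 |
| 1.00 throughout | 1.000 | 1.000 |
| 1.30 throughout | 1.000 | 1.000 |
| 0.70 rising steadily to 0.85 over months 1-12 | 1.018 | 1.018 |
| 0.70 to month 6, then fading to 1.00 at month 12 | 1.000 | 1.061 |
| 0.95 falling to 0.70 by month 6, then held | 0.941 | 1.000 |

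In the fifth row the levels in months 7-12 are 0.74, 0.79, 0.84, 0.89, 0.94 and 1.00. STOP has fewer days in every month but the last, while the printed value is (1.00/0.70)^(1/6) = 1.061. Restoring b1 returns the level ratios exactly.

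A simulation agreed: 300 trials of 300 participants at a constant ratio of 0.70, with participant-level variation but no PCP clustering, fitted by Poisson regression. The mean printed values were 1.000 and 1.000, and the median level ratio at month 6 was 0.70.

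**4. The plan's own scenarios.** The SAP gives 90-day means, not monthly paths. The two quarters are centred three months apart, so the per-month slope ratio is approximately (second-quarter ratio / first-quarter ratio)^(1/3).

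| Scenario | Quarter ratios | 180-day level ratio | Slope ratio per month |
|---|---|---|---|
| 1 constant | 14/20 = 0.700; 14/20 = 0.700 | 28/40 = 0.700 | 1.000 |
| 2 waning | 14/20 = 0.700; 15/20 = 0.750 | 29/40 = 0.725 | 1.023 |
| 3 constant, assessment impact | 13/19 = 0.684; 12/18 = 0.667 | 25/37 = 0.676 | 0.991 |
| 4 waning, assessment impact | 13/19 = 0.684; 13/18 = 0.722 | 26/37 = 0.703 | 1.018 |

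**5. The template code.** The text calls time continuous, but the code lists it in CLASS. With time as a class variable both rows fail an estimability check; with time continuous both pass. Treatment is also in CLASS, with levels 0 and 1. Under the usual ascending order, 1 -1 is EUC minus STOP, the reverse of the text, so the fade in the fifth row of step 3 would print 0.942 instead of 1.061.

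**The case against.** The best defence is that this model was meant to describe trends, and a slope contrast does that. SAP 7.6 gives the durability question to the quarterly model, and Protocol 14.6 describes the monthly repeat as a way to understand temporal patterns. Level ratios for risky opioid use appear in Tables 43-45. For the other substances, SAP 7.8 sends analyses without time effects to the Section 7.2.2 model, and the 90-day and 180-day shells are repeated. Table 41 and the box plots show monthly use by arm, where a steady 30% benefit would be visible. SAP 7.6 says in words that it is comparing slopes, and the Table 42 footnote mentions slopes.

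Most of this stands, and it rules out some stronger readings. A reader might infer that the plan would report a lasting benefit as harm, or never report a level effect; the quarterly and 180-day models contradict both. A reader might also carry over the sentence "A risk ratio less than 1 would indicate fewer days of risky opioid use for those assigned to STOP", but SAP 7.2.2 says that of the primary model, not of Table 42. Nor does every constant effect print exactly 1.00: Scenario 3, a constant difference in days against a falling control mean, gives 0.991.

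Two things are left unanswered. No inferential level ratio is planned for the 30-day outcome, although SAP 7.5 lists it under a fewer-days hypothesis and SAP 7.6 says this model evaluates the treatment effect. And one column heading carries two different quantities in neighbouring tables.

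**Conclusion.** The point holds as a gap in reporting and labelling for the monthly 30-day analyses. As written, Table 42 and its four repeats cannot separate a constant proportional benefit from no effect or from constant harm. Under the plan's waning scenarios they would print about 1.02 per month while STOP has roughly 27% to 30% fewer days over 180 days (ratios 0.725 and 0.703).

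This rests on the text's definition: time continuous, STOP relative to EUC, knot at month 6. The scenario figures are approximations from two 90-day means. The planning scenarios stop at month 6, so every Months 7-12 value above is illustrative. The affected results are supportive or secondary. The primary analysis and the quarterly durability analysis are untouched. The change should be made, but nothing in the main conclusion depends on it.

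**What to change.** 1. In Table 42 and Tables 47, 51, 55 and 59, head the existing column as the ratio of monthly slopes, STOP/EUC, per month. Replace the term risk ratio for this quantity in SAP 7.6 to match.
2. From the same fitted model, add STOP/EUC level rate ratios that include the treatment term at a small named set of months, for example 3, 6, 9 and 12. Mark them as supportive and not adjusted for multiplicity, in line with SAP 9.0. With time continuous, treatment levels ordered 0, 1 and the knot at month 6, the month 9 row would be `treat -1 1 treat*time -9 9 treat*timespl -3 3`. Levels at named months keep their meaning if the data-driven knot moves, though the spline coefficient must then be recalculated.
3. In the same edit, take time out of CLASS and set the sign of the existing contrasts so that they estimate STOP versus EUC.

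The cost is a short code and table-shell edit, plus four further unadjusted estimates in each of five tables (4 × 5 = 20), some of which overlap the 90-day and 180-day ratios. The slope results are kept.
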